Additionally, the clinically validated University of Pennsylvania Smell Identification Test (UPSIT) (Sensonics International, Haddon Heights, NJ) was administered to determine whether participants had anosmia/hyposmia. The UPSIT is a 40-item, self-administered "scratch-and-sniff" test that uses microencapsulated odorants that are released by scratching designated spaces on a paper test booklet. Summed scores were used to evaluate olfactory function and identify/exclude participants with undiagnosed smell loss or total anosmia (summed UPSIT score ≤ 18).

Following enrollment, participants were randomly assigned to a sequence of two sessions using a computer-randomized order created by an investigator who was not a member of the field team. To control participants inhalation exposures to terpenes in the forest air, participants wore a powered air-purifying respirators (PAPRs; 3M[™] Versaflo[™] Powered Air Purifying Respirator, TR-800-PSK/94248; 3M, St. Paul, MN). In one session, the PAPR mask was fitted with a particle-only filter (3M[™] Versaflo[™] High-Efficiency Filter, TR-6710N-5) to allow for the inhalation of forest terpenes ("terpenes-on"). In the other session, the mask was fitted with a charcoal filter (3M[™] Versaflo[™] Organic Vapor/HEPA Cartridge, TR-6510N) that removed particles, terpenes, and other BVOCs from the breathing zone ("terpenes-off"). Equipment labels were covered and filters were labeled "A" (later revealed to be "terpenes-off") to blind the study field team and participants to treatment assignment. A washout period of at least eight days between sessions was included to reduce carryover effects (Sibbald & Roberts, 1998).

Forest-sitting sessions took place at the UW Charles L. Pack Experimental Forest located near Eatonville, Washington ("Pack Forest") during June to September 2022 and 2023 to avoid rain, snow, and cold weather. The sessions were 60 minutes each and took place between 10:00 AM and 4:00 PM in a stand of old- and second-growth Douglas Fir, Western Red Cedar, and other conifers accessible by a 10-minute drive on an unpaved single-lane road from the Pack Forest Conference Center. Participants were seated in a comfortable chair, but the session was otherwise unscripted.

3. Methods

We enrolled 43 adult participants between July 12, 2022, and September 21, 2023. Our target sample size of 40 participants was based on the estimated numbers needed to detect minimum differences in the study

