# 2. Specific Aims

2. 1. Aim 1. Assess whether VOC inhalation regulates stress reduction and affective outcomes of the terpenes-on vs. terpenes-off sessions.

Primary physiological outcome: increases in the HF (ms) component of HRV.

Secondary outcomes: decreases in blood pressure, heart rate, self-reported stress, negative affect, and levels of inflammatory cytokines (IL-6, TNF-alpha, CRP) and cortisol in serum, and increases in positive affect, measured via mobile physiology equipment and blood using standard clinical methods.

Hypothesis: VOC inhalation will regulate increases in the HF (ms) component of HRV and decreases in blood pressure, heart rate, self-reported stress, and levels of inflammatory cytokines in serum as secondary outcomes.

2. 2. Aim 1a. Assess the degree of association of absorbed dose of seven forest-derived VOCs in serum (i.e.,  $\alpha$ - pinene,  $\beta$ -pinene,  $\beta$ -myrcene,  $\Delta$  3- carene, limonene,  $\beta$ - carophyllene,  $\alpha$ -humulene) with these outcomes.

Hypothesis: Absorbed dose of seven forest-derived VOCs in serum will be associated with stress reduction and affective outcomes.

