# 3.3 Absorbed Dose Association with Outcomes

We will calculate the association of absorbed dose (difference between baseline and T4 serum terpene levels) and the difference between baseline measurements and time point 4 (T4) for ln-HF HRV, skin conductance levels, self-reported stress, positive and negative affect levels (SF-PANAS), systolic blood pressure, diastolic blood pressure, heart rate, inflammatory biomarkers, and cortisol using a mixed effect model. Participants who completed only one session will also be included in analysis.

For ln-HF HRV, skin conductance levels, self-reported stress, systolic blood pressure, diastolic blood pressure, heart rate, inflammatory biomarkers, and cortisol:

$$Y_{is} = \beta_0 + \beta_1 baseline_{is} + \beta_2 absorbed dose_{is} + \alpha_i + \varepsilon_{is}$$

Where:

- $Y_{is}$  is the observed average outcome for individual *i* at T4, and session *s* where *s* is session 1 or session 2
- $\beta_0$  is the average  $Y_{is}$  for the study population at T4, adjusted for baseline.
- $\beta_1$  is the estimated difference in  $Y_{is}$  at T4 between two groups differing in baseline by 1 unit, adjusted for absorbed dose.
- $\beta_2$  is our primary coefficient of interest and is the estimated difference in  $Y_{is}$  between two groups differing in absorbed dose by 1 unit, adjusted for baseline.
- $\alpha_i$  is the random intercept for subjects to account for repeated measures within individuals
- $\varepsilon_{is}$  is the observation-specific error

For positive and negative affect levels (SF-PANAS):

 $Y_{is} = \beta_0 + \beta_1 baseline_{is} + \beta_2 absorbeddose_{is} + \beta_3 missingscale item_{is} + \alpha_i + \varepsilon_{is}$ 

Where:

- $Y_{is}$  is the observed average outcome for individual *i* at T2, and session *s* where *s* is session 1 or session 2
- $\beta_0$  is the average  $Y_{is}$  for the study population at T2, adjusted for baseline, missing scale items, and absorbed dose.
- $\beta_1$  is the estimated difference in  $Y_{is}$  at T2 between two groups differing in baseline by 1 unit, adjusted for missing scale items and absorbed dose.
- $\beta_2$  is our primary coefficient of interest and is the estimated difference in  $Y_{is}$  between the two groups differing in absorbed dose by 1 unit, adjusted for baseline and missing scale items.

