#### 4.2 Data Exclusion Criteria

Five participants were removed from analysis: two participants who were recommended for exit by IRB staff following responses to study protocols, one participant who withdrew mid-session, and two participants who were found to meet exclusion criteria following their first session.

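### The Aim 1a model has one absorbed-dose coefficient that mixes within-person and between-person dose slopes; the two should be estimated separately

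*SAP*

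**What the plan says.** Aim 1a (SAP section 2) reads "Assess the degree of association of absorbed dose of seven forest-derived VOCs in serum" with the trial outcomes. SAP section 3.3 defines absorbed dose as the change in serum terpene level from baseline to T4, giving one value per person and session. Each model contains the baseline outcome, absorbed dose and a subject term that "is the random intercept for subjects to account for repeated measures within individuals". The affect models add the number of missing items.

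The dose coefficient β₂, named as the one of main interest, is the outcome difference "between two groups differing in absorbed dose by 1 unit, adjusted for baseline". Section 3.3 also states: "Participants who completed only one session will also be included in analysis".

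The models contain no person-mean dose, no centring, no fixed subject effect, no filter or period term, and no person-level covariate other than baseline. The sensitivity analyses elsewhere in the SAP deal with censored IL-6 values (the primary-analysis section, 3.2) and missing data (4.1), not with this.

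On design, Protocol section 2 says that "participants were randomly assigned to a sequence of two sessions using a computer-randomized order". So filter order was randomised; absorbed dose was not.

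**The concern.** Dose varies for two different reasons. Within a person it varies mainly because one session used the terpene-removing filter and the other did not, and the order was random. Between people it varies with uptake, metabolism and exposure conditions, none of which was randomised. A random-intercept model with a single dose term treats the two slopes as equal and averages them. If they differ, β₂ describes neither comparison, and its value depends on the dose spread and the ICC.

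The documents themselves make a person-level common cause plausible. Eligibility excludes a short list of drugs because they influence terpene metabolic pathways and short-term inflammatory biomarkers, which is one factor acting on both exposure and outcome. Other such factors may remain. One of them could create or mask a dose association, although a crossover can remove stable person-level confounding with the data already in hand.

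**Working it through.** **Plan's own figure.** There is none for Aim 1a. The only design figure is the target of 40 participants, and it cannot be reproduced because the documents give no Hedges' g, SD, alpha or power.

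**Inputs from the documents**
- Protocol section 3: "We enrolled 43 adult participants between July 12, 2022, and September 21, 2023".
- SAP 4.2: "Five participants were removed from analysis". So 43 − 5 = 38 analysed.
- SAP 4.1: 138 rumination questionnaires. The text there implies two per session, so 138 / 2 = 69 sessions.
- If all 69 sessions belong to the 38, then p + s = 38 and 2p + s = 69, which gives p = 31 pairs and s = 7 singles. This is an inference, not a stated count.

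**Assumptions.** Dose is near zero with terpenes-off. Terpenes-on dose is scaled to mean 1 with between-person CV c of 0.3 to 0.8. The residual ICC r (given baseline) is 0 to 0.7. Correlation of dose with baseline is ignored.

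**Information on β₂, in units of 1 / within-person residual variance**
- Within pairs: W = 31(1 + c²)/2
- Between pairs: B = 31 × 2 × (c²/4) × (1 − r)/(1 + r)
- Singles: S = 7 × [0.5(1 + c²) − 0.25] × (1 − r) = 7 × [0.25 + 0.5c²] × (1 − r)

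In S, the 0.25 is the on/off filter contrast, which is randomised for singles too, barring selective dropout. Only the 0.5c² part reflects uptake. The non-randomised share is therefore [B + 7 × 0.5c² × (1 − r)] / (W + B + S).

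| c | r | W | B | S | Uptake part of S | Share |
|---|---|---|---|---|---|---|
| 0.3 | 0.7 | 16.90 | 0.25 | 0.62 | 0.09 | 1.9% |
| 0.3 | 0.3 | 16.90 | 0.75 | 1.45 | 0.22 | 5.1% |
| 0.3 | 0 | 16.90 | 1.40 | 2.07 | 0.32 | 8.4% |
| 0.8 | 0.7 | 25.42 | 1.75 | 1.20 | 0.67 | 8.5% |
| 0.8 | 0.3 | 25.42 | 5.34 | 2.79 | 1.57 | 20.6% |
| 0.8 | 0 | 25.42 | 9.92 | 3.99 | 2.24 | 30.9% |

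The range is about 2% to 31%, or about 2% to 21% for r between 0.3 and 0.7. If the between-person slope were zero, β₂ would understate the within-person slope by roughly this share. If it were equal and opposite, the shortfall would be about twice the share (about 4% to 41% for r between 0.3 and 0.7).

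**Simulation check.** The section 3.3 model was compared with one that splits dose into person mean and deviation. Settings: 31 pairs and 7 singles, off-session dose 10% of on-session dose, true dose effect zero, c of 0.25, 0.5 or 1.0, ICC 0.2 or 0.5 before the trait below is added, and 300 runs per setting. Let k be the outcome shift, in residual SDs given baseline, per SD of a stable uptake trait. Coefficients are in residual SDs per unit of average on-session dose.
- k = 0: single coefficient −0.01 to +0.03, so no bias.
- k = 0.3: +0.07 to +0.16.
- k = 0.5: +0.08 to +0.25.
- Within-person coefficient after the split: −0.02 to +0.03 in every setting (Monte Carlo error about 0.01).
- Cost at k = 0: the SD of the dose coefficient rises from 0.14–0.23 to 0.16–0.24.

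**The case against.** The strongest reply is that Aim 1a asks only about a degree of association, for which a precision-weighted pooled slope is a legitimate summary, and that nothing in the documents shows the two slopes to differ. This stands in part. Read strictly as association, the problem is a coefficient that is hard to interpret; it becomes bias when β₂ is read as a dose effect. A reader might infer that Aim 1a is meant to prove that absorbed terpenes drive the response. The documents do not say so, and Protocol section 4 puts the focus on the olfactory pathway.

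A reader might also count everything that one-session participants contribute as confounded. That gives a share of 4.9% (c = 0.3, r = 0.7) to 35.4% (c = 0.8, r = 0), but it misclassifies their randomised on/off contrast. The top of the range also needs an ICC of zero, which leaves little room for a stable person-level confounder, so r between 0.3 and 0.7 is the more coherent range.

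Some protection already exists: dose is a change score, the session's baseline outcome is in the model, listed drugs were excluded and terpene sources were restricted for 24 hours. These measures reduce person-level confounding but do not rule it out.

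Finally, the within-person slope is not a randomised dose comparison. Ambient air on the day varies by session and so enters the deviation too. With off-session dose near zero, 1/(1 + c²), or 61% to 92%, of the within-person information is simply filter on versus off, which Aim 1 already estimates. Differences in uptake are much of what sets Aim 1a apart, and that is a good reason to report the person-mean coefficient as well.

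**Conclusion.** The point holds as a conditional one. Section 3.3 blends two slopes, and nothing in the SAP separates or compares them. If a stable person-level factor affects both uptake and the T4 outcome given baseline, β₂ is biased as a dose effect; if none does, there is no bias. The documents do not show which case applies.

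The non-randomised between-person share is a minority, about 2% to 31% (about 2% to 21% at ICC 0.3 to 0.7). It rests on the assumed dose CV, ICC and near-zero off-session dose, and on the inferred 31 pairs and 7 singles. The documents do not support a stronger conclusion that the Aim 1a result will be wrong or that Aim 1 is compromised: the Aim 1 comparison uses the randomised filter directly.

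**What to change.** In each section 3.3 model, replace the single dose term with two: the participant's mean dose over the sessions attended, and the session's deviation from that mean. Report both coefficients. Base any dose-effect interpretation of Aim 1a on the deviation (within-person) coefficient, and label the person-mean coefficient observational.

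State two limits in the SAP:
- One-session participants have a deviation of zero and so inform only the person-mean dose term. Their mean is a single session's dose and depends on which filter they drew.
- Centring removes stable person-level confounding but not session-level confounding.

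The cost is one extra term per model, slightly wider intervals for the dose coefficient, and a within-person estimate that overlaps substantially with the Aim 1 filter contrast. No new data are needed.

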## 4. Data Exclusions

## 4.1 Handling Missing Data

We assessed missing data after obtaining a blinded dataset but before being unblinded to the actual treatment per session. Unexpected missing data emerged in the blinded dataset, resulting in the absence of a predefined approach to address this issue prior to data collection. Primary analysis will use a complete case dataset, except for the positive and negative affect outcome. 16 (3.9%) of the 414 questionnaires

were missing 1-2 items at one of the time points, and the impact of missing items will be adjusted for using the number of missing items variable in the model.

We expect the small amount of missingness to have a minimal impact on our results, however we will assess this impact with sensitivity analyses. For comparison, we will perform the analysis on an imputed dataset. We expect this to narrow confidence intervals without greatly impacting the coefficient.

We will be imputing some missing values for two types of data, 1) missing questionnaire items (relevant to secondary outcomes) and 2) missing baseline ln-HF HRV (relevant to primary outcome). The PANAS positive affect (PA) and negative affect (NA) outcomes are scored by summing 5 individual PA and NA items. 16 (3.9%) of the 414 questionnaires were missing 1-2 items at one of the time points, though the data were typically complete for other time points. Because answers for the same item are modestly correlated between timepoints from the same day (mean  $R^2 = 0.58$ ), but still performed better than other imputation approaches (random PA and NA item from the day, mean PA or NA score, and regression imputation), we will use the mean available item value for missing items. This methodology is similar to the mean imputation approach demonstrated in Shrive et al. (2006), but employs individual item row mean imputation, a single item imputation approach that can be used for longitudinal data (Engels and Diehr, 2003).

Brief State Rumination Inventory (BSRI) is a sum of 8 individual items. 6 (4.3%) of the 138 questionnaires were missing 1-2 items. The answers for the same item were correlated with the other time point for the same day (mean  $R^2 = 0.83$ ).

For ln-HF HRV, there were 5 participants whose ln-HF HRV was partially captured both before and during exposure, but missing during the window of our standard baseline time (i.e., B1).

Additional 5-minute periods of ln-HF HRV were calculated using continuous data from before treatment exposure, including 10-5 minutes before B1 (R1), 5-0 minutes before B1 (R2), 0-5 minutes into the venipuncture procedures (V1), 5-10 minutes into the venipuncture procedure (V2), 0-5 minutes into the drive up to the forest site (D1), and 5-10 minutes into the drive up to the forest site (D2).

Correlations between B1 ln-HF HRV and each additional time point prior to exposure were assessed using a complete case data set.

Time points with the highest correlations (R1, R2, V1, D1) were included in single linear regression models to predict B1 values using a complete case data set. One participant did not have any additional timepoints available, so we used a regression model with the B1 measurement from the other session as a predictor ( $s_{b1}hrv \sim s_{b1}hrv$ ).

Each single linear regression model (b1\_hrv ~ r1\_hrv, b1\_hrv ~ r2\_hrv, b1\_hrv ~ v1\_hrv, b1\_hrv ~ d1\_hrv, s2\_b1\_hrv ~ s1\_b1\_hrv) was cross validated using a complete-case dataset to assess  $R^2$  values (0.92, 0.95, 0.98, 0.85, and 0.83, respectively).

Models were preferentially ranked based on R^2 values and predicted values for B1 will be imputed depending on R1, R2, V1, D1, and S1B1 (session 1 baseline 1) timepoint availability. Of the missing

baseline observations, there is one person for whom we would use V1 to predict B1, three people for whom we would use D1 to predict B1, and one person for whom we would use S1B1 to predict S2B1.

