### 3.2 Primary Analysis: Linear Mixed Effect Model

We will calculate the main effect of the filter on the difference between baseline measurements and time point 2 (T2) for ln-HF HRV, skin conductance levels, self-reported stress, positive and negative affect levels (SF-PANAS) and timepoint 4 (T4) for systolic blood pressure, diastolic blood pressure, heart rate, inflammatory biomarkers, and cortisol using a mixed effect model. Systolic blood pressure, diastolic blood pressure, heart rate, inflammatory biomarkers and cortisol data were collected at T4, but not T2. As the machine values for left-censored IL-6 observations are closest to the true values, machine values will be used for censored observations for the primary analysis. Sensitivity analyses will be performed for the IL-6 analysis by comparing model output using machine values to model output using limit of detection and zero and a logistic regression using a detect/non-detect variable. If using a different approach for imputing IL-6 changes the results substantially, then our result is not easily interpretable. Participants who completed only one session will also be included in analysis. Analyses will be conducted in R (version 4.3.1; R Core Team, 2023) using the lme4 R package (Bates et al., 2015). We will present the main effect results and associated statistics, including effect sizes and confidence intervals.

For ln-HF HRV, skin conductance levels, self-reported stress, positive and negative affect levels (SF-PANAS):

$$Y_{is} = \beta_0 + \beta_1 baseline_{is} + \beta_2 filter_{is} + \alpha_i + \varepsilon_{is}$$

Where:

•  $Y_{is}$  is the observed average outcome for individual *i* at T2, and session *s* where *s* is session 1 or session 2

- $\beta_0$  is the average  $Y_{is}$  for the study population at T2 when they were assigned the A filter, adjusted for baseline.
- $\beta_I$  is the estimated difference in  $Y_{is}$  at T2 between two groups differing in baseline by 1 unit.
- $\beta_2$  is our primary coefficient of interest and is the estimated difference in  $Y_{is}$  between the A filter and the B filter at T2, adjusted for baseline.
- $\alpha_i$  is the random intercept for subjects to account for repeated measures within individuals
- $\varepsilon_{is}$  is the observation-specific error

For systolic blood pressure, diastolic blood pressure, heart rate, inflammatory biomarkers, and cortisol:

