- $Y_{is}$  is the observed outcome for individual *i*, at time point *t* where *t* is T4, and session *s* where *s* is session 1 or session 2
- $\beta_0$  is the average  $Y_{is}$  for the study population at T4 when they were assigned the A filter, adjusted for baseline.
- $\beta_1$  is the estimated difference in  $Y_{is}$  at T4 between two groups differing in baseline by 1 unit.
- $\beta_2$  is the average difference in  $Y_{is}$  between the A filter and the B filter, adjusted for baseline.
- $\alpha_i$  is the random intercept for subjects to account for repeated measures within individuals
- $\varepsilon_{is}$  is the observation-specific error

For positive and negative affect levels (SF-PANAS):

$$Y_{is} = \beta_0 + \beta_1 baseline_{is} + \beta_2 filter_{is} + \beta_3 missingscale item_{is} + \alpha_i + \varepsilon_{is}$$

Where:

- $Y_{is}$  is the observed average outcome for individual *i* at T2, and session *s* where *s* is session 1 or session 2
- $\beta_0$  is the average  $Y_{is}$  for the study population at T2 when they were assigned the A filter, adjusted for baseline and missing scale items.
- $\beta_1$  is the estimated difference in  $Y_{is}$  at T2 between two groups differing in baseline by 1 unit.
- $\beta_2$  is our primary coefficient of interest and is the estimated difference in  $Y_{is}$  between the A filter and the B filter at T2, adjusted for baseline and missing scale items.
- $\beta_3$  is the estimated difference in  $Y_{is}$  between two groups differing in missing affect scale items by 1 item, adjusted for baseline.
- $\alpha_i$  is the random intercept for subjects to account for repeated measures within individuals
- $\varepsilon_{is}$  is the observation-specific error

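### SAP 3.3 states the affect dose analysis at T4 but defines the SF-PANAS dose model at T2; separately, the scoring of incomplete SF-PANAS forms is not stated.

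*SAP*

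**What the plan says.** **Dose model (SAP 3.3).** The introduction relates the serum terpene change to the change from baseline to T4 in each outcome, and names positive and negative affect among them. Exposure is defined as "absorbed dose (difference between baseline and T4 serum terpene levels"). The first model, for the non-affect outcomes, defines its terms at T4. The second, for SF-PANAS, defines Y, β0 and β1 at T2.

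**Timing (Protocol 3, Methods).** Affect was assessed at T1 (0-5 min), T2 (17.5-22.5 min), T3 (37.5-42.5 min) and T4 (55-60 min). The second blood sample was taken at T4.

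**Missing affect items (SAP 4.1 and 3.2).** The "outcomes are scored by summing 5 individual PA and NA items". Affect is exempt from the complete-case rule, and for the 16 of 414 forms that lack one or two items "the impact of missing items will be adjusted for using the number of missing items variable in the model". SAP 4.1 continues: "For comparison, we will perform the analysis on an imputed dataset", and "We expect this to narrow confidence intervals without greatly impacting the coefficient". Further down it adds that "we will use the mean available item value for missing items".

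In SAP 3.2 the equation with baseline and filter only is introduced as applying "for ln-HF HRV, skin conductance levels, self-reported stress, positive and negative affect levels (SF-PANAS"). A later equation for SF-PANAS alone adds β3, the difference "between two groups differing in missing affect scale items by 1 item, adjusted for baseline".

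**The concern.** **Time point.** Two analysts following SAP 3.3 could fit different affect dose models, one at T4 from the introduction and one at T2 from the equation. The T2 version relates an outcome to a serum change that is completed only after the outcome was recorded. Affect at T2 cannot respond to terpenes absorbed later, so that slope is not the baseline-to-T4 association that Aim 1a is said to estimate. It also could not be set beside the blood pressure, HRV, stress or biomarker slopes from the same section, which are at T4.

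**Incomplete forms.** The number entering the affect model for an incomplete form is undefined. It could be the sum of the answered items, a prorated sum or an imputed sum. The count could cover T2 only, baseline and T2, or the whole session. In the longitudinal models it carries the session subscript only, but so do the time indicators, so the notation does not settle this.

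**Working it through.** **1. SAP 3.3 side by side**

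| Element | Time point |
|---|---|
| Introduction, affect named | T4 |
| Definition of absorbed dose | baseline to T4 |
| Model for non-affect outcomes | T4 |
| Model for SF-PANAS: Y, β0, β1 | T2 |

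Three of the four agree. One possible reason for T2 is that SAP 3.2 uses it for the filter effect on affect. However, SAP 3.2 also uses T2 for ln-HF HRV, skin conductance and self-reported stress, and SAP 3.3 moves all three to T4. The link with SAP 3.2 therefore does not explain an exception for affect.

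**2. Timing**

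- Shortest gap from the end of T2 to the start of the T4 window: 55 − 22.5 = 32.5 min.
- Share of the session after the T2 window: (60 − 22.5)/60 = 62.5%.
- The documents do not give the ratio of a T2 slope to a T4 slope. As illustrations only: if affect responds in proportion to elapsed exposure, the window midpoints give 20/57.5 = 0.35; if the response is complete by T2, the ratio is 1; if it fades after T2, the ratio exceeds 1. The ratio is treated as unknown.

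**3. Extent of incomplete forms**

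- 16/414 = 3.86%, which reproduces the SAP's 3.9%.
- 414/6 = 69 and 138/2 = 69 (the rumination forms), so 69 sessions is a plausible inference. It is not certain: the protocol describes five affect assessments per session (baseline and T1-T4), 414/5 = 82.8 is not whole, and a sixth form is not explained.
- With 69 sessions, about 16/414 × 69 = 2.7 T2 forms would be incomplete, so a T2 count slope would rest on about three sessions.
- Items run from 1 to 5, so each gap lowers a raw sum by 1 to 5 points. One linear slope can correct that only on average, and a T2 count does not repair a lowered baseline score.

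**4. Does the scoring rule matter?** The T2 filter model was simulated with 4,000 trials per subscale. Taken from the documents: 43 − 5 = 38 participants, 16 incomplete forms with one or two gaps, reliability .86 (positive affect, PA) and .40 (negative affect, NA; 0.41 achieved), and same-item R² 0.58. Assumed: 31 participants with two sessions and 7 with one, item means 2.7 (PA) and 1.2 (NA), R² 0.58 for both subscales, and gaps at random over the ten items. Mean standard errors (SE) of the filter effect, with the change from full data:

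| Scoring | PA | NA |
|---|---|---|
| Full data | 0.506 | 0.171 |
| Same-item mean imputation, no count | 0.503 (−0.6%) | 0.171 (0.0%) |
| Raw sum + T2 count | 0.518 (+2.4%) | 0.178 (+4.1%) |
| Raw sum + session count | 0.530 (+4.7%) | 0.184 (+7.6%) |
| Imputed + T2 count | 0.507 (+0.2%) | 0.172 (+0.6%) |
| Prorated, no count | 0.507 (+0.2%) | 0.173 (+1.2%) |
| Complete cases | 0.518 (+2.4%) | 0.176 (+2.9%) |

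Full data is the benchmark because single imputation treats filled-in values as observed; its PA SE falls below that of full data. Mean bias was below 0.003 points throughout. The root-mean-square departure from the full-data estimate was 0.13 (T2 count) and 0.18 (session count) for raw PA sums, against 0.03 for imputation. For NA the figures were 0.05 and 0.08 against 0.01.

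A separate run of 400 trials with other assumed item means (3.0 and 1.3) gave, for raw sum + T2 count, 0.439/0.422 = +4.0% and 0.347/0.341 = +1.8%.

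**The case against.** **On the dose model.** T2 may simply have been carried over from the SF-PANAS equation in SAP 3.2, in which case an analyst would follow the introduction and use T4. That is plausible, but it is an inference. The equation is the operative specification, and three of its terms say T2. The objection limits the seriousness of the conflict without removing it. A reader might also infer that T2 is wrong for affect throughout. The documents do not support that: SAP 3.2 chooses T2 deliberately for the filter effect, and nothing here bears on that choice.

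**On missing items.** Here the case on the other side is strong, and several tempting readings fail.

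- *The count adjustment is an inferior primary method.* This holds only if answered items are simply summed, which the SAP never says. Its sentence on using the mean available item value allows imputed sums plus the count, and then almost nothing is lost.
- *The SAP contradicts its own ranking of methods.* It does not. SAP 4.1 ranks same-item imputation above a random item, a mean score and regression imputation. It does not compare it with a count covariate.
- *The second SF-PANAS equation in SAP 3.2 overrides the first.* The SAP does not say which one governs.
- *The filter effect would be biased.* With random gaps it is not. In a deliberately extreme run with every gap in one filter condition, the raw sum with a T2 count gave 1.17 against 0.96 with full data (PA-like items), and imputation gave 0.94. The documents give no split of the gaps by filter, so this shows what could happen and is not a finding.

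The SAP also recognises the gaps, expects little effect and already plans the imputed run. Whether imputation or the count should be primary is largely a matter of preference.

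**Conclusion.** The T2/T4 conflict in SAP 3.3 is an error as written. It rests on the text alone and needs no assumption. Its direct consequence is an Aim 1a affect slope that does not match the stated question or the exposure definition. The numerical effect cannot be derived from the documents.

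The missing-item point is an omission and minor. There are two primary affect equations, no scoring rule for an incomplete sum and no stated scope for the count. Relative to full data, the SE cost is about 2% to 8% if answered items are simply summed and about 1% or less if scores are imputed or prorated. These figures depend on the assumed item parameters, the session split and random gaps. Affect is a secondary outcome, and the primary HRV outcome is untouched. Overall severity is minor.

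**What to change.** 1. In SAP 3.3, define Y, β0 and β1 of the SF-PANAS dose model at T4, in line with the section's introduction, dose definition and companion model. The missing-item count, if kept, should refer to the forms that enter that model.
2. In SAP 3.2, keep one primary equation for SF-PANAS, with or without the count, and list affect only there.
3. In SAP 4.1, state how an incomplete five-item sum is scored in the primary, longitudinal and dose models, and which time points the count covers. The planned same-item mean imputation is one ready choice. If it is used, note that its values are treated as observed, which slightly understates the SE.

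The cost is wording only: affect was collected at T4 and the imputed dataset is already planned. Protocol 2 (Design) already reports which condition label A stood for, so the changes should be dated. If affect dose models have already been fitted at T2, both versions should be reported and the T2 version labelled as such.
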